9.3.6 Number and Length of Hospital Readmission for an Acute Complication of Cirrhosis

All occurrences of hospital admissions are collected via eCRF through Month 12 and will be listed.

For each subject, the number of hospital readmissions due to acute complication of cirrhosis will be counted. This endpoint will be presented by treatment as a continuous variable and analyzed by Poisson regression with adjustment for overdispersion using the Pearson statistic to estimate the scale parameter. The total number of hospital admissions in the SMT + Albutein 20% treatment group will be compared to the SMT alone. The response variable in the model will be the total number of hospital admissions experienced by a subject while on treatment. The model will include treatment group, IWRS stratification factors of region (Europe or North America) and history of hospitalization for acute decompensation of liver cirrhosis (yes or no) as factors. The logarithm of the subjects' treatment duration will be used as an offset variable in the model to adjust for subjects having different exposure times during which the events could occur. The estimated treatment effect (ie, the incidence rate ratio of SMT + Albutein 20% versus SMT alone) and corresponding 95% confidence interval (CI) will be presented.

Hospital readmissions occurring on treatment are defined as any hospital admission that occurred with a start date/time on or after the subjects treatment start date/time (treatment start date/time is defined as; date/time of randomization (for SMT alone group) or commencement of Albutein (SMT+ Albutein treatment group) treatment). If time is missing and the incidence occurred on or after the date of randomization (for SMT alone group) or the date of commencement of Albutein (for SMT+ Albutein treatment group) treatment it will be considered to have occurred while on treatment. If the hospital readmission is on-going at the end of the study, it is also considered as occurring on treatment.

Number	BIG-CL-SP-000319		
	Version	2.0	Status
Effective Date	09-Sep-2024	Page	37 of 52
Effective			
GRIFOLS			
Bioscience Industrial Group			

In the event a hospital readmission occurs prior to treatment start date and the discharge date is after the treatment start date it will be counted as an occurrence.

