For each subject, the total duration (days) of hospital readmission for acute complication of cirrhosis will be calculated as the sum of the durations of each readmission (discharge date – admission date + 1) due to acute complication of cirrhosis. Descriptive statistics will be presented by treatment and analyzed by analysis of covariance (ANCOVA) with adjustment for stratification factors. If a subject's hospital readmission is considered on-going at the end of the study, the end of study completion date will be used to calculate the duration of the hospital readmission.

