9.3.7 Number and Length of ICU Admission

For each subject, the number of hospital readmissions in which the subject was admitted to the ICU will be counted. This endpoint will be presented by treatment as a continuous variable and analyzed in the same way as hospital readmissions using Poisson regression with adjustment for over dispersion using the Pearson statistic to estimate the scale parameter.

ICU admission occurring on treatment are defined as any ICU admission that occurred with a start date/time on or after the subjects date/time of randomization (for SMT alone group) or commencement of Albutein (SMT+ Albutein treatment group) treatment. If time is missing and the incidence occurred on or after the date of randomization (for SMT alone group) or the date of commencement of Albutein (for SMT+ Albutein treatment group) treatment it will be considered to have occurred while on treatment.

In the event a ICU admission occurs prior to treatment start date, and the discharge date is after the treatment start date, it will be counted as an occurrence and the duration of this ICU admission will be calculated as [(discharge date – treatment start date) + 1].

For each subject, the total duration (days) of hospital readmission to the ICU will be calculated as the sum of the durations of each ICU admission (ICU discharge date – ICU admission date + 1). Descriptive statistics will be presented by treatment and analyzed by ANCOVA with adjustment for stratification factors. If a subject's ICU admission is considered on-going at the end of the study, the end of study completion date will be used to calculate the duration of the ICU readmission.

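### SAP 9.3.6 counts a hospital stay open at treatment start and measures it from admission, unlike 9.3.7, and no sentence keeps the index hospitalization out of the readmission endpoint

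*SAP*

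**What the plan says.** SAP 9.3.6 (exploratory: number and length of hospital readmission for an acute complication of cirrhosis) contains these rules.

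- Data: "All occurrences of hospital admissions are collected via eCRF through Month 12 and will be listed".
- On-treatment definition: a readmission on treatment is "defined as any hospital admission that occurred with a start date/time on or after the subjects treatment start date/time". Treatment start is randomization in the SMT arm and the first infusion in the SMT + Albutein arm.
- Model: "The response variable in the model will be the total number of hospital admissions experienced by a subject while on treatment". The model is an overdispersed Poisson regression with log treatment duration as offset.
- Exception: "In the event a hospital readmission occurs prior to treatment start date and the discharge date is after the treatment start date", the stay counts as an occurrence. No duration rule is attached.
- Length: the total "will be calculated as the sum of the durations of each readmission", each taken as discharge date − admission date + 1. The only special case is a stay still open at the end of the study.

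SAP 9.3.7 makes the same exception for an ICU stay open at treatment start, but there "it will be counted as an occurrence and the duration of this ICU admission will be calculated as" discharge date − treatment start date + 1.

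SAP 5.1 and Protocol 4.2 put screening inside the hospitalization for acute decompensation. They require randomization within 72 hours of screening and allow it before or after discharge.

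**The concern.** There are two linked problems.

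**Length.** Adjacent sections treat the same situation differently. The 9.3.6 formula brings days before treatment start into an endpoint defined as on-treatment. It also departs from the section's own definition, which requires the stay to start on or after treatment start. The numerator can then hold an event whose onset lies outside the exposure period used as offset. Elsewhere the SAP keeps such events apart: paracenteses count only from treatment start (9.2.6), and a TIPS insertion before treatment start is a baseline occurrence (9.3.10).

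**Index stay.** A subject randomized in hospital and discharged on a later date has a stay that began before treatment start and ended after it. Its cause, acute decompensation, can satisfy the qualifier about an acute complication of cirrhosis. Neither document says that this stay is not a readmission. If it is among the recorded admissions, the exception taken literally counts it. The readmission count, its rate ratio and the length of stay would then include an event that both arms brought into the trial.

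**Working it through.** The plan states no figure for this endpoint, so there is nothing to reproduce. The check applies the two length rules to the same dates and then follows the count. The dates are illustrative; the rules are the SAP's.

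**Step 1, length in general.** Let A be admission, T treatment start and D discharge, with A < T < D.

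- 9.3.6: D − A + 1
- 9.3.7 rule: D − T + 1
- Difference: (D − A + 1) − (D − T + 1) = T − A

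The excess is exactly the time in hospital before treatment, whatever the discharge date.

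**Step 2, index stay, if it is in the data.** Admitted 1 March, treatment start 10 March, discharged 14 March, never readmitted:

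| Rule | Count | Length (days) |
|---|---|---|
| 9.3.6 as written | 1 | 14 − 1 + 1 = 14 |
| 9.3.6 with the 9.3.7 length rule | 1 | 14 − 10 + 1 = 5 |
| Index stay excluded | 0 | 0 |

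The 9 excess days (14 − 5 = 10 − 1) depend on the chosen dates. With assumed gaps of 3, 7, 14 or 21 days between admission and treatment start, the excess is 3, 7, 14 or 21 days. Changing the length rule alone does not correct the count.

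**Step 3, true readmission, if the index stay is not in the data.** The subject must be discharged after in-hospital screening and readmitted before treatment start, all inside the randomization window.

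- Readmitted 8 March: 14 − 8 + 1 = 7 days against 5, an excess of 2.
- Readmitted on the screening date, 7 March, three days before treatment start: 14 − 7 + 1 = 8 against 5, an excess of 3.

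So the excess is at most about 3 days. It is 2 if the window is read, as SAP 5.1 also puts it, as three days including the day of randomization. SAP 12 says earlier protocol versions allowed a longer gap, so the excess could be larger for subjects enrolled under them.

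**Step 4, direction of the effect on the rate ratio, if the index stay is counted.** Let R be the true rate ratio, m the SMT mean number of true readmissions, and s the share of subjects whose index stay is counted. Take s as the same in both arms, and exposure as equal.

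- Apparent ratio = (R·m + s) / (m + s)
- Apparent ratio − R = s(1 − R) / (m + s)

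For s > 0 the apparent ratio lies between R and 1, which is dilution.

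**Step 5, size.** The documents give neither m, nor R, nor the share randomized in hospital, so the size cannot be derived. As an illustration on assumed values only, take R = 0.70:

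- m = 1, s = 0.50: (0.70 + 0.50) / 1.50 = 0.80
- m = 2, s = 0.25: (1.40 + 0.25) / 2.25 = 0.73
- m = 0.5, s = 0.75: (0.35 + 0.75) / 1.25 = 0.88

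Over m from 0.5 to 2 and s from 0.25 to 0.75 the range is 0.73 to 0.88.

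**The case against.** The best defence is the word readmission. The section title, the counting sentence, the exception and the length paragraph all use it, as do the protocol objective and variable, and in ordinary usage an index admission is not a readmission. The two phrases in 9.3.6 that speak of admissions are limited to stays starting on or after treatment start or occurring on treatment. The eCRF is not among the documents, and the protocol's visit lists and schedule name no hospital-admission item, so its scope cannot be inferred.

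Much of this stands. A reader might infer that the plan is shown to miscount index stays. The documents do not support that, because whether the index stay is recorded on the admission page is unknown. But the word alone is a weak safeguard. Given in-hospital screening and a 72-hour window, hardly any stay other than the index stay can be open at treatment start, so a programmer could reasonably apply the exception to it. For subjects in the stratum with an earlier hospitalization for acute decompensation, the index stay is itself a readmission in everyday language. The nearest text that sets the initial discharge apart is a footnote on SAE seriousness in Protocol 8.3.7, which does not define this endpoint.

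A reader might also infer a bias in either direction, because discharge after treatment start follows randomization in an open-label trial. That goes too far. Treatment is scheduled to start on the day of randomization, so being an inpatient at that moment is settled before allocation. Allocation can matter only at the margin, for example for discharge on that same day. Nothing in the documents points to a material imbalance, and dilution is the expected effect.

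**Conclusion.** The point holds, at minor severity.

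The text alone establishes that 9.3.6 counts a stay begun before treatment start against its own on-treatment definition, measures it from admission, and so differs from 9.3.7 by the number of days between admission and treatment start. It also establishes that no sentence excludes the index hospitalization.

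The consequence for the count is conditional. If the index stay is in the admission data, subjects who are never readmitted can score 1, and the exploratory rate ratio is expected to be diluted. That direction assumes similar shares in both arms, which randomization makes likely. If the index stay is not in the data, only the length mismatch remains. It is confined to rare readmissions within the screening window and amounts to at most about 3 days each under the current 72-hour rule.

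The endpoint is exploratory and outside the fixed testing sequence. The primary analysis, the secondary analyses and the sample size do not depend on it.

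**What to change.** Make three wording changes in the SAP.

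1. In 9.3.6, state that the index hospitalization (the stay during which the subject was screened) is not a readmission and adds neither to the count nor to the length.
2. In 9.3.6, for a true readmission open at treatment start, keep the count and take the length as discharge date − treatment start date + 1, as in 9.3.7. Say explicitly that this is an exception to the on-treatment definition.
3. In 9.3.7, reword the opening, "For each subject, the number of hospital readmissions in which the subject was admitted to the ICU will be counted", so that it counts ICU admissions. That matches the section's own definition, "defined as any ICU admission that occurred with a start date/time on or after the subjects date/time of randomization", and the variable in Protocol 7.1.3. Without this, change 1 could remove ICU admissions that begin on treatment during the index stay, which should be kept.

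The cost is one exclusion sentence, one duration clause and one reworded sentence. Programmers need to check whether the index stay appears in the eCRF admission data and how to identify it. No new data are needed, and the model and offset stay as they are.

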9.3.7 Number and Length of ICU Admission

For each subject, the number of hospital readmissions in which the subject was admitted to the ICU will be counted. This endpoint will be presented by treatment as a continuous variable and analyzed in the same way as hospital readmissions using Poisson regression with adjustment for over dispersion using the Pearson statistic to estimate the scale parameter.

ICU admission occurring on treatment are defined as any ICU admission that occurred with a start date/time on or after the subjects date/time of randomization (for SMT alone group) or commencement of Albutein (SMT+ Albutein treatment group) treatment. If time is missing and the incidence occurred on or after the date of randomization (for SMT alone group) or the date of commencement of Albutein (for SMT+ Albutein treatment group) treatment it will be considered to have occurred while on treatment.

In the event a ICU admission occurs prior to treatment start date, and the discharge date is after the treatment start date, it will be counted as an occurrence and the duration of this ICU admission will be calculated as [(discharge date – treatment start date) + 1].

For each subject, the total duration (days) of hospital readmission to the ICU will be calculated as the sum of the durations of each ICU admission (ICU discharge date – ICU admission date + 1). Descriptive statistics will be presented by treatment and analyzed by ANCOVA with adjustment for stratification factors. If a subject's ICU admission is considered on-going at the end of the study, the end of study completion date will be used to calculate the duration of the ICU readmission.

9.3.8 Incidence of Disease-Related Complications

GRIFOLS	Number	IG1601	Big-CL-SP-000319	Version	2.0	Status	Effective	Effective Date	09-Sep-2024	Page	38 of 52
	IG1601 Statistical Analysis Plan										

All disease-related complications will be collected via a eCRF through Month 12 and will be listed.

The number and percentage of subjects with at least one occurrence of each of the following disease-related complications from the list below on or after treatment start date will be presented by treatment, and compared using the generalized linear models implemented in SAS GENMOD procedure, in which the odds ratio and corresponding 95% Confidence Interval (CI) will be determined from a logistic model, with the incidence of disease related complication (Yes/No) as the dependent variable and treatment, stratification factors of region (Europe or North America) and history of hospitalization for acute decompensation of liver cirrhosis (yes or no) as factors. The robust variance estimate for the treatment effect will be estimated based on the compound symmetry working correlation structure. If the model does not converge, first-order autoregressive (AR (1)) working correlation structure will be used. If it fails to converge, the independent working correlation structure will be used.

Anticipated disease related complications will include:

- HE – including HE I, HE II, HE III, and HE IV
- GI Bleeding – including lower GI bleeding and upper GI bleeding
- Portal Hypertension
- Ascites
- Spontaneous Bacterial Peritonitis
- Hyponatremia
- HRS – including Type 1 and Type 2
- Other (includes disease related complications not captured in the types listed above)

In addition, the number of each type of disease-related complications will be counted for each subject and presented by treatment as a continuous variable and as a categorical variable with categories 0, 1, 2, 3, 4 or more. No analysis of treatment differences will be performed.

9.3.9 Serum Albumin Concentration and Albumin Functional Capacity in Serum (Albumin Binding Capacity)

Serum albumin concentration and albumin binding capacity are analyzed by a central laboratory, with all results and normal ranges reported in SI units. Serum albumin concentration is measured before and after each infusion at each visit during the treatment period; albumin binding capacity is measured once per visit.

Serum albumin concentration and albumin binding capacity will be listed for each subject, and summarized by visit. A summary table will present descriptive statistics for original values and change from baseline by treatment, parameter and visit. For the SMT + Albutein 20% group and serum albumin concentration parameter, change from baseline to the pre-infusion timepoint will be summarized. Moreover, the difference between pre-infusion and post-infusion within each visit will also be summarized.

GRIFOLS	Number	IG1601	Version	2.0	Status	Effective	Effective Date	09-Sep-2024	Page	39 of 52
	IG1601	Statistical Analysis Plan								

In addition, change from baseline at each visit will be analyzed for visits with data collected for both treatment groups, in the same way as CLIF-C OF scores. Figures will be presented for means over time including the baseline visit for both albumin concentration and functional capacity.

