7.1.3 Exploratory Variables

- Incidence of ACLF (3, 6, and 12 months)
- Organ function subscores (liver, renal, cerebral, coagulation, circulation, and respiration), according to the CLIF-C OF score and the total CLIF-C OF score (Appendix 3)
- Number and length of hospital readmission for an acute complication of cirrhosis
- Number and length of ICU admission
- Incidence of disease-related complications (see Section 8.3.10)
- Serum albumin concentration and albumin functional capacity in serum (albumin binding capacity [Table 7-1])
- Incidence of insertion of TIPS for refractory ascites
- CLIF-C ACLF score ,CLIF-C AD score, MELD score, and Child Pugh score
- Quality of life: EQ-5D-5L health questionnaire (Appendix 5)

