9.1.2.3 Exploratory Endpoints

As appropriate to the data, the original values or changes from baseline (last measurement taken prior to the start of study treatment on Day 1) of the following exploratory endpoints will be listed for each subject, summarized by treatment group, and compared between treatment groups by means of ANCOVA or Student's t tests (for normally-distributed variables), non-parametric Mann-Whitney U test (for non-parametric variables), Kaplan-Meier estimates and Log-rank test (for time-to-event variables), Poisson regression model (for count variables), and Fisher's exact test or Chi-square test (for binomial variables):

Incidence of ACLF, CLIF-C OF score, CLIF-C ACLF score, CLIF-C AD score, MELD score, Child Pugh score, number and length of hospital readmission for an acute complication of cirrhosis, number and length of ICU admission, incidence of disease-related complications, serum albumin concentration, albumin functional capacity (albumin binding capacity), incidence of insertion of TIPS for refractory ascites, and the EQ-5D-5L health questionnaire.

For the normally-distributed variables, the ANCOVA model will include change from baseline as the dependent variable, treatment as a fixed factor, and baseline value as a covariate. If any potential confounders are identified among subjects' baseline characteristics, they will be included as additional covariates in the ANCOVA models to adjust treatment effects. In addition, for the longitudinal measurements taken repeatedly over time, the treatment effects may be explored by using the mixed-effect model repeated measures analysis.

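### For complication types that recur often, SAP 9.3.8's yes/no comparison wastes the counts it derives and ignores unequal follow-up; an exploratory rate model would be a cheap addition

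*SAP*

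**What the plan says.** SAP 9.3.8 collects disease-related complications through Month 12. The tabulated measure is "The number and percentage of subjects with at least one occurrence of each of the following disease-related complications". The arms are compared by a logistic model "with the incidence of disease related complication (Yes/No) as the dependent variable and treatment, stratification factors of region" and history of hospitalization. No offset, follow-up time or visit term is listed.

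The same section then says that "the number of each type of disease-related complications will be counted for each subject and presented by treatment as a continuous variable", and also in categories from 0 to 4 or more. It closes: "No analysis of treatment differences will be performed".

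Other counts are handled differently. Readmissions (SAP 9.3.6) are "analyzed by Poisson regression with adjustment for overdispersion using the Pearson statistic to estimate the scale parameter", with the log of treatment duration as offset. Paracenteses (9.2.6) get the same model, and ICU admissions (9.3.7) are analysed in the same way as readmissions. Protocol 9.1.2.3 includes "Poisson regression model (for count variables)" among its methods for exploratory endpoints.

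Protocol 7.1.3 names this variable "Incidence of disease-related complications (see Section 8.3.10)". It is exploratory, has no stated power and lies outside the fixed testing sequence.

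**The concern.** Two features of the yes/no comparison raise questions.

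1. **The cut at one.** A subject with one episode of encephalopathy and a subject with six count the same. If albumin lowers the episode rate without keeping many subjects wholly free of episodes, the yes/no comparison has little chance of showing it. Protocol 2.3 gives fewer decompensation episodes as one route by which albumin might help. Protocol 8.3.10 treats these events as disease progression rather than adverse events unless the drug is suspected, so SAP 9.3.8 is where they are compared as a class.
2. **No allowance for time at risk.** Observation of complications is cut short by death. The trial is designed on the premise that albumin reduces death or transplant. If so, albumin subjects are observed for longer, and a yes/no outcome without an offset counts that extra time against albumin.

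What is at stake is the reading of an exploratory result. Error control for the primary and secondary endpoints is not affected.

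**Working it through.** **Inputs from the documents.** 205 per arm, two-sided 5%, primary events 46% vs 31% at one year, 20% dropout (SAP 6.2, 6.5; Protocol 9.2).

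**Assumptions.** The documents give no complication rate, dispersion or effect. I take control rates μ of 0.1 to 3 per subject-year, gamma frailty variance k (the negative binomial dispersion) of 0 to 4, and a rate ratio of 0.70.

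**The plan's own figures reproduce.** A two-proportion calculation for 46% vs 31% at 80% power gives 165 per arm, or 413 after 20% dropout, against 410 stated. Power with 205 × 0.8 = 164 per arm is 80.0%. The hazard ratio is ln 0.69 / ln 0.54 = 0.6022, as stated.

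**Step 1: cost of the cut alone, full follow-up in both arms.**
- Yes/no: P(any) = 1 − (1 + kμ)^(−1/k), with a Wald test of the log odds ratio.
- Count: Wald test of the log rate ratio, with variance (1/μ + k)/205 per arm.

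Example, μ = 1 and k = 1:
- Yes/no: 50.0% vs 41.2%, log odds ratio −0.357, SE 0.199. Power = Φ(0.357/0.199 − 1.96) = 43%.
- Count: variance (2 + 2.429)/205 = 0.0216, SE 0.147. Power = Φ(0.357/0.147 − 1.96) = 68%.

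| Control rate per year | Yes/no, k = 1 | Count, k = 1 | Gain in points, k = 0 to 4 |
|---|---|---|---|
| 0.1 | 16% | 17% | 1–2 |
| 0.2 | 24% | 27% | 2–4 |
| 0.5 | 37% | 50% | 9–12 |
| 1 | 43% | 68% | 16–25 |
| 2 | 41% | 81% | 19–40 |
| 3 | 37% | 86% | 26–49 |

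Simulation with follow-up cut short equally in both arms (54% event-free at one year) gives similar gaps: 3–4 points at 0.2, 17–24 at 1 and 21–41 at 2 per year.

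**Step 2: a different treatment effect.** Suppose treatment changes only whether any episode occurs (40% vs 28%), with equal counts among those affected. The order then reverses: yes/no 72–74%, count 27–55%.

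**Step 3: unequal follow-up.** Mean event-free time in the year is 0.46/0.616 = 0.747 years for SMT and 0.31/0.371 = 0.835 for albumin, about 12% more, before dropout.

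Now set the complication rate ratio to 1. With total exit hazard L (primary event plus dropout, −ln 0.8 = 0.223) and k = 1, P(any) = ∫ from 0 to 1 of e^(−Lt) μ/(1 + μt)² dt. At μ = 1:
- SMT: L = 0.839, P(any) = 37.1%.
- Albumin: L = 0.594, P(any) = 40.3%.
- Odds ratio 1.14, log 0.133, SE 0.203. The chance of a significant result favouring SMT is Φ(0.133/0.203 − 1.96) = 9.6%.

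Over 0.1 to 2 per year this chance is about 4% to 11%, against 2.5% nominal. Without dropout, simulation gives 5.8% to 13.9% over 0.2 to 2 per year. A rate model with a follow-up offset stays at about 2% to 3% when frailty is independent of death.

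**Step 4: separating the two effects.** Simulation with rate ratio 0.70, 1 per year, k = 1 and no dropout gives 37% vs 61% (yes/no vs count) with equal survival, and 15% vs 62% with hazard ratio 0.6022. Of the 47-point gap in the second case, 24 points are the cut at one. The other 23 are the missing follow-up adjustment.

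**The case against.** The strongest defence is that the yes/no analysis follows the endpoint. The protocol calls this variable an incidence, while it names readmissions and ICU admissions by number and length and paracenteses by total number. The SAP treats other incidence endpoints (refractory ascites, ACLF, TIPS) as proportions, and SAP section 12 classes this one with binary or ordinal outcomes. A reader might infer that the SAP breaks the protocol by not modelling the counts. The documents do not support that: the protocol's list of methods applies as the data require. This defence stands against a charge of inconsistency. It does not answer the power or follow-up points.

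Two other strong readings also fail. The first is that the endpoint as a whole loses much of its power, with ascites and encephalopathy close to saturation. No rate is given for any type, so the documents cannot show which types recur often enough. The second is that recurrences are discarded. They are shown by arm, and related burden is tested as rates through readmissions, ICU admissions and paracenteses. Those cover only episodes leading to admission or drainage, however.

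The counts have weaknesses of their own. The trial is open-label, and the albumin arm has 23 infusion days that SMT subjects do not attend (SAP 5.2.4). Neither document says how one episode of a persistent state, such as ascites, portal hypertension or hyponatremia, is separated from the next. Counts depend on this more than yes/no does.

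The rate model is not free of bias either. If the same frailty raises both complications and death, it too falsely favours SMT: about 4% to 13% in one set of simulations and 4.8% to 27.8% in a harsher set, where yes/no gave 9.9% to 29.2%. These limits stand and belong with the proposal.

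**Conclusion.** The point holds in a conditional form. For types recurring at about 0.5 per subject-year or more, with a roughly constant rate ratio, the yes/no comparison gives up about 10 to 40 points of power (up to 49 at 3 per year). For rare types the loss is a few points. Where treatment mainly prevents a first episode, there is no loss and yes/no is the better test.

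Separately, if the planned survival benefit is real, the logistic model is tilted towards SMT. The 4% to 11% rests on frailty variance 1, 0.1 to 2 episodes per year, 20% dropout and exponential times. This part needs no assumption that episodes recur, only that survival differs.

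All complication rates here are mine. Because the endpoint is exploratory and unpowered, this is a worthwhile low-cost improvement and not a defect in the trial's main inference.

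**What to change.** In SAP 9.3.8, replace the sentence "No analysis of treatment differences will be performed" with a rate model for each recurring complication type:

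- **Model:** overdispersed Poisson as in SAP 9.3.6, or negative binomial, or a rate regression with robust variance.
- **Terms:** treatment and the two IWRS stratification factors.
- **Offset:** log of time from randomization to death, transplant or last complication follow-up, with episodes counted over the same interval.
- **Report:** rate ratio and 95% CI beside the existing odds ratio, labelled exploratory.

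State which types count as recurring and how separate episodes of persistent states are identified.

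Cost: one SAP sentence and one more model per type, on counts already derived and with a model family already programmed. SAP 6.5 plans no multiplicity adjustment beyond the fixed sequence, so nothing there changes.

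Three limits should be stated with the result: the model assumes a common effect on first and repeat episodes; it relies on episode recording in an open-label trial with unequal contact; and it reduces but does not remove bias from frailty shared with death. Keeping the odds ratio beside it covers the case where the effect is mainly on first episodes.
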